2. To determine which women in this FDCS cohort are most at risk of preterm birth.
3. To identify which women with a previous CS in established labour are most likely to benefit from a cervical cerclage.

Investigating the mechanism underpinning the increased risk of PTB/LM will aid our understanding of risk in women with a history of FDCS only and inform current and future treatment strategies. We will recruit 30 women with a CL of $> 25\text{mm}$ and 30 women with a CL of $\leq 25\text{mm}$ (short cervix). Women with a short cervix will be participants of the main RCT. Half of these women will have had a cervical cerclage as part of their management.

GLOSSARY OF TERMS

FDCS	Fully dilated caesarean section
CS	Caesarean section
MRI	Magnetic Resonance Imaging
PTB	Preterm Birth
LM	Late miscarriage
TAC	Transabdominal cerclage
CL	Cervical length
qfFN	Quantitative fetal fibronectin

1. Introduction

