3.3. CRAFT-IMG

This is a prospective cohort sub-study collecting image data and outcomes in a sub-group of women participating in CRAFT-OBS (n=30) and CRAFT-RCT (n=30).

The subgroup will be recruited from participants attending University College London and St Thomas' Hospital only. All participants will have experienced FDCS in a previous pregnancy and will include women with and without cervical shortening in the current pregnancy based on their CL monitoring. Participants will be allocated to one of three groups: a) women with cervical length of <25 mm who have been randomised to cerclage in CRAFT-RCT (n=15), b) women with cervical length of <25 mm who have been randomised to observation in CRAFT-RCT (n=15), c) women with cervical length of ≥ 25 mm.

A transvaginal ultrasound using a new enhanced protocol developed by [name] at UCL will be undertaken in all women. This procedure is more detailed than standard measurement of CL. The site of previous scar tissue and any other abnormalities (for example the presence of cysts) will be recorded. Serial MRIs will also be performed. Recruited patients will have up to 3 serial transvaginal ultrasounds and MRIs during their pregnancy.

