4.3. CRAFT-IMG

Primary endpoint:

- i. Alterations in imaging parameters between women with a full dilatation C-section in a previous pregnancy and either a cervix $\leq 25\text{mm}$ or a cervix $>25\text{mm}$ in this pregnancy which culminates in a preterm (<37 week) delivery.

5. Sample size and power calculation

All power calculations were performed by the trial statistician [name].

CRAFT-OBS: With estimated prevalence of 15% preterm birth rate prior to 37 weeks, and 16.2% of all deliveries being by emergency caesarean section; we will require data on 2200 women to estimate the event rate to 10% relative accuracy (e.g. 13.5% to 15.6%).

An average district general hospital has 4,000 deliveries per year, of which 648 (16.2%) might be by Emergency Caesarean. We aim to recruit 324 of these (50%) at a minimum of 7 study sites. At St Thomas' Hospital rather fewer deliveries (11%) are caesareans in labour; so we will aim for at least 20 sites, taking the assumptions above into account.

If we acquire data of cervical length and/or quantitative fetal fibronectin in this cohort, we will be able to validate these prediction tools. If we treat a short cervix of $\leq 25\text{mm}$, and a raised qfFN of $\geq 50\text{ng/ml}$ as positive tests, we anticipate a 75% sensitivity and 83% specificity from the literature for both tests (16).

Assuming 10% event rate, 1000 women (100 cases and 900 controls) would allow use to estimate the sensitivities of qfFN and CL to within 10% and the specificities to within 3% of the true value. The PPV would be estimated within 7% and NPV within 1.5% of their true values.

CRAFT-RCT: Pilot data indicates that at least 10% of all births and 70% of preterm births associated with FDCS occur before 34 weeks. In order to detect a reduction in this rate from 10% to 5% 474 women are required in each group to give 80% power. We will aim to recruit 500 in each arm in order to allow for 5% loss to follow-up.

CRAFT-IMG: We consider that the participation of 60 women in this sub-study will provide useful information for planning future research; this is achievable by recruiting at 2 sites (UCLH and St Thomas' Hospital): 30 women with cervix $>25\text{mm}$ and 30 women with cervix $\leq 25\text{mm}$ (15 women with cerclage, 15 women without).

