Serial MRI scans will be performed on a 3-Tesla MRI scanner at St Thomas' Hospital. Conventional imaging will include high resolution T1 and T2 weighted images as well as diffusion datasets. The first advanced protocol transvaginal ultrasound and MRI will occur at any time from 20 weeks gestation. Where delivery has not occurred, further imaging will be offered (up to a maximum of 3 MRI and 3 of these transvaginal ultrasound scans).

Outcome data: All participants' data will be collated up until postnatal discharge. Neonates will be followed up until discharge or 28 days (whichever is sooner). Prompts on the database will alert the research midwife/assistant when each trial participant reaches her delivery date. Birth registers and in-patient records will be used to track hospital admissions and pregnancy outcomes. Outcome data (medical and economic) will be collected by review of NHS Maternity and medical records. If information is unavailable, e.g. if the delivery occurred elsewhere, the patient, patient's GP or other hospital will be contacted. Gestational age will be calculated using Study Protocol: **Cerclage After Full-dilatation caesarean-section**

IRAS ID:261294

REC: REC 19/LO/1270

Version 2.0

Date: 10.09.19

ultrasound estimated date of delivery predicted at the 12-15 week ultrasound scan. The primary and secondary outcome data will be collected from hospital records after discharge from neonatal care.

Source data and documents will be accessible by the research team only and any paper records will be stored in a locked cabinet in the Principal Investigators' offices. Electronic versions of these source documents are stored on Trust computers only and behind the NHS firewall. The study may be subject to inspection and audit by King's College London and Guy's and St Thomas' NHS Foundation Trust under their remit as sponsor and co-sponsor respectively, and other regulatory bodies to ensure adherence to GCP and the NHS Research Governance Framework for Health and Social Care.

The identifiable information obtained as part of this study will be managed in accordance with the General Data Protection Act (2018). The computerised information is protected by a software and hardware barrier, and the records are handled in the same way as hospital records. Data will be stored for 25 years in Trust firewalls/KCL Firewalls in accordance with legal requirements for the storage of maternity records.

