CRAFT-IMG: This sub-study will provide data on relationships between macro/ micro-structural cervical defects in pregnant women who have had a previous FDCS and a short cervix ≤ 25 mm, compared with those who have a cervix > 25 mm. Comparison will be made between the two groups. Relative efficiency of detection of cervical defects by MRI (and relationships with outcomes), will be compared to those identified by ultrasound. We will also assess changes in the cervix over time. This will be performed in conjunction with senior statistician [name]. Images will be assessed for: overt structural abnormalities in collaboration with radiologists using a structured proforma. Patients and clinicians will be informed of clinically significant findings. These images will be compared to TVUS images in order to ascertain whether there is any correlation in findings between the two modalities (ref 910).

Ultrasound data will be analysed contemporaneously at acquisition. MRI data will be assessed for cervical anatomical features and presence and location of overt lesions or disruptions on conventional imaging (blinded to the participant's history). Models will be fitted using the open-source toolkits for diffusion data by [name] and [name] (UCL)^{10,11}, to obtain quantitative maps of tissue composition and microstructure properties. We will analyse the different imaging findings between short and long cervixes and correlate it with their perinatal outcomes.

9. Study Governance

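### The CRAFT-IMG analysis pools short-cervix women with and without cerclage, so its short-versus-long, change-over-time and outcome results can be confounded by the suture

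*Combined protocol and SAP*

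**What the plan says.** The design and analysis sections group the imaging participants differently.

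- **Section 3.3 (CRAFT-IMG):** "Participants will be allocated to one of three groups". These are short cervix randomised to cerclage (15), short cervix randomised to observation (15), and long cervix.
- **Section 5 (sample size):** 30 long and 30 short, the short group being "15 women with cerclage, 15 women without". The Professional Summary agrees: "Half of these women will have had a cervical cerclage as part of their management".
- **Section 4.3 (endpoint):** "Alterations in imaging parameters between women with a full dilatation C-section in a previous pregnancy and either a cervix" at or below 25 mm or above it, in a pregnancy ending before 37 weeks. Cerclage is not mentioned.
- **Section 8 (data analysis):** short is set against long, with the sentence "Comparison will be made between the two groups". It closes: "We will analyse the different imaging findings between short and long cervixes and correlate it with their perinatal outcomes". Change across serial scans is also to be assessed. No part of the CRAFT-IMG paragraph mentions cerclage.

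On timing, section 7.3 says "The first advanced protocol transvaginal ultrasound and MRI will occur at any time from 20 weeks gestation". Cervical length surveillance runs from 14+0 to 23+6 weeks (section 7.3), and an allocated cerclage is due no more than a week after the short cervix is found (section 7.1). No section says whether the first research scan comes before or after the suture.

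**The concern.** Half the short group is allocated a procedure on the organ being imaged, and almost none of the long group would be expected to have it. If a suture shifts a measured parameter, such as a diffusion value, a dimension or its trajectory, part of that shift enters the short-minus-long difference. Serial scans add to this, because the suture normally stays in until about 37 weeks. Later scans in that arm will then usually show a sutured cervix even where the first did not.

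The outcome correlation has a second problem. Cerclage is given to prevent preterm birth, so in the pooled short group it may alter both the image and the outcome. An association, or the lack of one, could then reflect treatment rather than the defect.

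At stake is the mechanistic reading of the sub-study and its use in planning later research. The RCT comparison and CRAFT-OBS are not affected.

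**Working it through.** **1. The plan's own figure.** 15 + 15 + 30 = 60, which agrees with section 5. The plan gives no alpha, power, SD or effect size for CRAFT-IMG, so there is no power statement to reproduce.

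**2. Order of suture and first scan.** The earliest research scan is at 20+0 weeks and cerclage is due within 7 days of diagnosis. 20+0 minus 7 days = 19+0. A diagnosis before 19+0, treated on schedule, therefore means a suture before any research scan. From 19+0 to 23+6 either order is possible. By calendar, 14+0 to 18+6 is 35 of the 70 days in the window. That is a share of days, not of women, since no distribution of gestation at diagnosis is given.

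**3. Size of the bias.** Assumptions, none of them in the documents: SD 1 in every group, no true short-long difference, two-sided 5% test. Let s be the suture effect in SD units and f the share of the 15 cerclage women with a suture in place at the scan. A fraction q = 0.5 × f of the short group is shifted by s, so

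bias = 0.5 × f × s.

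The variance in the short group becomes 1 + q(1 − q)s², and SE = √[(1 + q(1 − q)s²)/30 + 1/30]. For f = 1 and s = 1: bias = 0.50, SE = √(2.25/30) = 0.274, bias/SE = 1.83, and the chance of a significant result is about 45% instead of 5%.

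| s (SD) | Bias, f = 1 | False-positive rate, f = 1 | Bias, f = 0.5 | False-positive rate, f = 0.5 |
|---|---|---|---|---|
| 0.5 | 0.25 | 16% | 0.125 | 8% |
| 1.0 | 0.50 | 45% | 0.25 | 15% |
| 1.5 | 0.75 | 73% | 0.375 | 26% |
| 2.0 | 1.00 | 89% | 0.50 | 38% |

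Simulation of 20,000 t-tests per case with f = 1 gave 15%, 43%, 73% and 92%. Comparing only the 15 unsutured short-cervix women with the 30 long-cervix women gave 5.0% to 5.2% throughout. If a true difference exists, the bias may inflate or mask it, depending on its direction.

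**4. Precision cost of separating the groups.** Detectable difference at 80% power = (1.960 + 0.842) × √(1/n₁ + 1/n₂).

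- 30 vs 30: 2.802 × √(1/30 + 1/30) = 0.72 SD
- 15 vs 30: 2.802 × √(1/15 + 1/30) = 0.89 SD
- 15 vs 15: 2.802 × √(1/15 + 1/15) = 1.02 SD

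At a true difference of 0.72 SD, power falls from 80% (30 vs 30) to 63% (15 vs 30).

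**The case against.** The best defence is that the plan already holds most of what is needed. Section 3.3 separates the arms, the Professional Summary names the relation of a defect to a cerclage as an interest, and section 7.3 records interventions including cerclage. The sub-study is exploratory and claims only that "We consider that the participation of 60 women in this sub-study will provide useful information for planning future research". This stands as a limit on severity and shows the repair is cheap. It does not answer the point, because section 8 and the endpoint drop the distinction.

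A second defence is anatomical. Section 1.1 places the vaginal cerclage in the distal cervix and the likely injury above it, so scar position relative to the internal os may be little disturbed. That is fair for scar location. It is less reassuring for quantitative tissue maps and change over time, since section 8 restricts neither to a region and has no rule for images containing a suture. Blinding MRI readers to history does not remove a physical effect on a measurement.

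Three stronger readings are tempting but unsupported:

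- **That suture effects will be mistaken for scar.** Radiologists read overt abnormalities on a structured proforma and may well recognise a suture. The documents show only that its handling is unstated.
- **That many cerclage women are first scanned after suturing.** Without a distribution of gestation at diagnosis, the number is unknown.
- **That cerclage versus no cerclage within CRAFT-IMG is a protected randomised comparison.** Section 7.1 describes these women as already randomised, at two sites, filling fixed quotas of 15. Selection after open allocation is possible, and rescue cerclage is permitted in both arms.

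**Conclusion.** The point holds as a mismatch between section 3.3 and section 8 that allows confounding by cerclage in three CRAFT-IMG analyses: the short-long contrast, change over time, and correlation with outcome. Bias of 0.25 to 1.00 SD (all sutured at the scan) or 0.125 to 0.50 SD (half sutured) follows only if the suture effect is 0.5 to 2.0 SD. That range is assumed; with no suture effect on a parameter, that parameter's structural contrast is not biased by this route.

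The detectable differences are benchmarks under an assumed two-sided 5% test and 80% power, not a test of any power claim in the plan. If the endpoint in section 4.3 is confined to pregnancies ending before 37 weeks, the usable numbers are smaller and all three figures are optimistic. This is a minor but worthwhile correction to an exploratory sub-study.

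**What to change.** Amend the CRAFT-IMG paragraph of section 8, and align section 4.3 with it:

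1. Carry the three groups of section 3.3 into the analysis.
2. Base the short-versus-long structural contrast on scans with no suture in place (women without cerclage, plus any pre-cerclage scans), or adjust for suture status at the scan.
3. Define suture status by what is actually present at each scan, counting rescue cerclage, not by allocation. Record it with the scan date.
4. Include suture status in the change-over-time and outcome models.
5. Report cerclage versus no cerclage among short-cervix women as exploratory, stating how and when imaging participants were selected relative to allocation.

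No change to scan timing, treatment or recruitment is needed. The cost is analysis wording and one recorded variable, probably derivable from dates already collected, together with lost precision. The detectable difference rises from 0.72 SD to up to about 0.89 SD if only the 15 women without cerclage contribute. Pre-cerclage scans would recover some of that; rescue cerclage before a scan would cost more. The 15 versus 15 comparison detects only about 1.02 SD and should be presented with its confidence interval.

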Preterm birth (PTB), birth before 37 weeks gestation, has a global prevalence of 9.6% and over a million annual neonatal deaths. Recently, it has been observed FDCS are associated with recurrent, early premature births and late miscarriage (LM). Over 25% of all deliveries in the UK are by caesarean section (CS) and at least one in seven of these occur at full dilatation, affecting 20,000 women per year. These women have a six-fold increased incidence of subsequent preterm birth compared with women who undergo 1st stage CS earlier in labour, which equates to 2500 women per year in the UK. In women who lose a pregnancy, more than half will also go on to experience recurrent pregnancy losses in spite of current intervention. Prediction and management of these cases requires further understanding of its aetiology, assessment of current prediction strategies as well as clinical management.

Despite the emerging association between FDCS and the risk of PTB/LM, the risk following an in labour CS, not at full dilatation, is unknown. It is thought that late stage caesareans, from 7cm onwards, are likely to carry some risk of future preterm birth (3). Furthermore, our current predictive models of preterm birth based on transvaginal ultrasound and quantitative fetal fibronectin are not validated in this specific cohort of women. In this CRAFT study we will evaluate the risk of preterm birth in women with a previous history of caesarean section in labour.

Clinically, a short cervix (≤ 25 mm) on transvaginal ultrasound scan (TVS) during the second trimester identifies women at high risk of PTB/LM. These women may benefit from prophylactic treatment such as a cervical cerclage but currently it is not part of routine care. At present it is unknown whether the ≤ 25 mm cut-off is a reliable predictive measure of risk in women following in labour CS. The mechanism of late miscarriage and early premature births < 34 weeks needs to be further understood with the imaging modalities available to us.

There will be three components to the CRAFT project: 1) CRAFT-OBS 2) CRAFT-RCT and 3) CRAFT-IMG Study

CRAFT-OBS: a study of risk and management in women with a history of CS in labour

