- If a woman is randomised to the standard care arm; she will have regular surveillance scans and clinic visits in accordance with local protocols and clinician practice. Rescue cerclage can be offered in cases of cervical opening with exposed membranes as per local guidelines. Targeted admission for bedrest and steroids can also be offered as per clinician experience and local protocols.

Concomitant medication during RCT

Participants are permitted to use any concomitant medication or treatment except progesterone alongside the trial management. This will be recorded at every visit on the RedCap database. Any other medication or treatment that would form normal clinical management for these women at risk of preterm labour i.e. antibiotics, corticosteroids, tocolytics etc. will be permitted according to the local hospital guidelines and clinician preference.

CRAFT-IMG

Participants will be identified from CRAFT-OBS (30 women with history of FDCS and cervical length >25mm) and CRAFT-RCT (30 women with FDCS and short cervix (\leq 25mm) by their direct care team. Interested women will be directed to have more information from the research team as well as confirmation of informed consent. 15 women from CRAFT-RCT will have been randomised to cerclage and the other 15 to standard management. Only women recruited at St Thomas' Hospital and UCLH will be eligible for this part of the CRAFT project. Doctors, sonographers or midwives in the research team will be recruiting patients to this sub-study.

All MRI scans will be performed at St Thomas' Hospital, and advanced protocol transvaginal ultrasound scans will be performed at both UCLH and St Thomas' Hospital. Repeat imaging will

be undertaken at regular intervals up to a maximum of 3 MRIs and 3 TVUS depending on patient availability in order to assess changes in the cervical tissue using the two imaging modalities.

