7.3. Data Collection

Following consent, data on the participant's demographic characteristics, risk factors, medical and obstetric history will be documented and entered onto the study specific database. This will include current and previous monitoring procedures and/or pregnancy interventions (e.g. cervical length measurements and cerclage). Cervical length will be measured with transvaginal

Study Protocol: **Cerclage After Full-dilatation caesarean-section**

IRAS ID:261294

REC: REC 19/LO/1270

Version 2.0

Date: 10.09.19

ultrasound in accordance with local protocols, measurements will be taken in triplicate and the shortest measurement used. Their pregnancy and neonatal outcomes will be collected from NHS patient records postnatally.

Participants with a history of FDCS will be referred to a preterm surveillance clinic where they will be invited for cervical length assessment (with or without other tests, such as fetal fibronectin) from 14+0 to 23+6 weeks gestation. Cervical length will be measured with transvaginal ultrasound in accordance with local protocols, measurements will be taken in triplicate and the shortest measurement used. If their cervical length is, or becomes ≤ 25 mm during this period they will be offered the opportunity to participate in CRAFT-RCT. Further explanation and a separate information sheet will be provided and additional consent form will be completed and stored as those for the main study. If the participant is unwilling to participate in this randomised controlled trial she will continue to be monitored and cared for as per local protocol/clinicians' experience, and continue in the observation arm of CRAFT study. Outcome data will be collected after the birth of her baby. Women who provide written informed consent will be randomised to either cervical cerclage or standard care.

Sixty participants, recruited at St Thomas' and UCLH, will be invited to have additional imaging tests for the sub-study, CRAFT-IMG. They will be given additional information and asked to sign another consent form, which will be stored as described above. These additional tests will involve serial transvaginal ultrasound measurements of cervical length and macro/microstructural changes as per [name] protocol and MRI scans of macro/microstructural cervical change.

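### CRAFT-IMG relates imaging findings to cervical length only as ≤25 mm versus >25 mm; adding a regression on length in mm would use 60 women better at almost no cost

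*Combined protocol and SAP*

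**What the plan says.** Section 8 (Data analysis, CRAFT-IMG) sets women with a cervix of ≤25 mm against women with a cervix of >25 mm, and adds: "We will analyse the different imaging findings between short and long cervixes and correlate it with their perinatal outcomes". The primary endpoint in section 4.3 uses the same split, "Alterations in imaging parameters between women with a full dilatation C-section in a previous pregnancy and either a cervix" of ≤25 mm or >25 mm, and ties it to a pregnancy ending in delivery before 37 weeks.

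Section 7.1 recruits to match: "30 women with history of FDCS and cervical length >25mm" from CRAFT-OBS, and "30 women with FDCS and short cervix" from CRAFT-RCT. Section 5 splits the short group ("15 women with cerclage, 15 women without") and justifies the total without a power calculation: "We consider that the participation of 60 women in this sub-study will provide useful information for planning future research".

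The Professional Summary says it is unknown whether the 25 mm "cut-off is a reliable predictive measure of risk in women following in labour CS". The Lay Summary says the same of women with previous FDCS, and section 1.2 adds that cervical length has not been validated in that group. Section 7.3 records length by transvaginal ultrasound: "measurements will be taken in triplicate and the shortest measurement used". The end of section 5 plans ROC curves for spontaneous preterm birth with length treated as continuous, if the data are available.

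**The concern.** Every woman in CRAFT-IMG must have a length in mm, because that is how she is placed in a group. The section 8 comparison then treats 8 mm and 25 mm as alike, and 25 mm and 26 mm as different, at a cut the project itself regards as open. With 60 women this gives up power to relate a quantitative MRI or ultrasound parameter to shortening. A two-group contrast also cannot show whether imaging findings change near 25 mm, at some other length, or gradually.

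**Working it through.** **The plan's own figure.** 30 + 30 = 60 and 15 + 15 = 30 agree. There is no alpha, power, effect size or SD from which to reproduce 60; it is a feasibility number.

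**Inputs.** From the documents: 30 women each side of 25 mm, with 15 of the short group having cerclage. Assumed, because the documents are silent: two-sided 5% level; length normal with mean 30–40 mm and SD 6–10 mm, with uniform alternatives; a continuous imaging parameter, linear in length, with normal error.

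**Information kept by the cut.** For a linear relation this is the squared correlation between length and the short/long indicator. With equal groups it is B/(B + W), where B = (m2 − m1)²/4, W = (v1 + v2)/2, and m and v are the mean and variance of length in each group.

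- Mean 35, SD 8: m1 = 21.17, m2 = 36.63, v1 = 10.99, v2 = 44.99. B = 15.46²/4 = 59.8 and W = 55.98/2 = 28.0, so 59.8/87.8 = 68.1% is kept and 31.9% lost.
- Whole normal grid: loss 20.6% (mean 40, SD 6) to 35.3% (mean 30, SD 10).
- Uniform examples: loss 15.1% (18–25 mm against 30–45 mm) to 32.5% (20–25 mm against 25–50 mm).
- Median split of a normal variable, for reference: 2/π = 63.7% kept, 36.3% lost; 60 × 0.637 ≈ 38 women.

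Hence roughly 15–36%.

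**Power for a 0.74 SD difference.** The correlation with group is d/√(d² + 4) = 0.74/√4.5476 = 0.347. The correlation with mm is 0.347/√(fraction kept). By Fisher's z with n = 60, power = Φ(√57 × atanh(r) − 1.96):

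| Analysis | r | Power |
|---|---|---|
| Two groups | 0.347 | 78% |
| mm, 79.4% kept | 0.389 | 87% |
| mm, 64.7% kept | 0.431 | 94% |

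Simulating the t-test and the regression directly (6,000 replicates per setting) gives slightly higher values: about 80% by groups and 91–95% using mm, except about 89% at the extreme corner (mean 40, SD 6). At 0.5 SD the simulated figures are about 46–49% and 57–66%.

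**With a cerclage term.** Only short-cervix women are randomised to cerclage, so the adjusted group contrast is in effect 15 women against 30. Its standard error is √(1/15 + 1/30) = 0.316 SD, against √(1/30 + 1/30) = 0.258 SD unadjusted, and 0.74/0.316 = 2.34. Simulated power is about 63–64% by groups. Using mm it is about 82–88%, except about 81% and 79% at means of 38 and 40 mm with SD 6. These figures are for the linear length term, without the curvature term.

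**Why cerclage matters here.** Section 7.1 has the procedure done within 7 days of shortening being found. Section 7.3 allows shortening to be found from 14+0 weeks and starts research imaging from 20 weeks. Cerclage can therefore precede the scan, and using a pre-cerclage length does not remove its effect on the image.

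**The case against.** The 25 mm boundary is a design feature. It is the CRAFT-RCT entry criterion and the source of the short group, and asking whether women who qualify at that threshold look different on imaging is legitimate even if the threshold is unvalidated. The sub-study is exploratory, and nothing in the protocol forbids an analysis in mm. All of that stands, which is why the two-group comparison should be kept. But the quota fixes how women are sampled, not how they must be analysed: regressing imaging on length remains valid when selection depends on length, provided the model form is right.

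A reader might infer three stronger points that the documents do not support.

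- *That a third of the information is lost.* That figure is near the top of a range resting on an assumed distribution and a linear relation. With a step at exactly 25 mm nothing is lost.
- *That measured length is discarded throughout.* Section 5 plans it as a continuous predictor in ROC curves. Those curves predict preterm birth, however; they do not relate imaging to length.
- *That regression should replace the primary endpoint.* Section 4.3 also involves preterm delivery, and the synopsis and section 2.2.3 aim at predicting it. Substituting an imaging–length regression would change the question.

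The power figures also do not carry over to the presence or absence of overt lesions, which is a substantial part of section 8.

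**Conclusion.** The point holds as a cheap improvement to the section 8 comparison. For a continuous imaging parameter linear in length, the cut costs roughly 15–36% of the information. At 0.74 SD that is the difference between about 80% and 89–95% power, or between about 63–64% and 79–88% once cerclage is in the model. The conclusion that mm is the better scale depends on a reasonably smooth relation; the size depends on a length distribution the documents do not give.

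**What to change.** In section 8 only:

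- For each quantitative imaging parameter, pre-specify a regression on cervical length in mm, with a cerclage term and one curvature term, as the analysis of the imaging–length relation.
- State which length is used: the pre-cerclage qualifying length for short-cervix women, and one defined length for long-cervix women, who may have several (for example, the measurement nearest enrolment in CRAFT-IMG).
- Keep the ≤25 mm versus >25 mm comparison alongside it, and leave the section 4.3 endpoint and its link to delivery before 37 weeks as they are.

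The group labels should be reconciled at the same time: sections 5, 7.1 and 8 use ≤25/>25 mm, section 3.3 uses <25/≥25 mm, and section 3.1 places exactly 25 mm on both sides.

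The cost is a few sentences of analysis text, with no extra women, scans or data. The downside is some loss of power if the true relation is a step at 25 mm; the retained two-group comparison and the curvature term limit that.
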